### 10.3 Participant Population(s) for Analysis

All participants' data will be analyzed, using an intent-to-treat approach. The sample size justification appears in Section 8 Study Participants.

### 10.4 Planned Interim Analysis:

There is no interim analysis planned. However, we are prepared, if requested by the Data Monitoring Committee at any point, to calculate interim statistical power for its review. Projections of interim power can be made under several scenarios for future data, including assumptions that current trends continue or that the future data reflect the relative effects used in the design of the trial. Safety reports will tally adverse events by intervention assignment and postulated relationship to the trial interventions; event rates will be reported per person year of follow-up. Should excessive risk to study participants be determined during the DMC review, the study will be stopped and all participants notified in a manner appropriate to the nature of the risk as defined by the IRB and DMC.

## 11. Data Collection, Handling and Record Keeping

### 11.1 Data Confidentiality

Every effort will be made to protect participant confidentiality. Research personnel will use only those parts of the medical record necessary to determine eligibility and follow the research protocol, and measures will be taken to maintain privacy during in-person sessions. We will establish ground rules at the group sessions, advising participants that they should only communicate information they feel comfortable communicating in public and that any information learned about other participants should be kept confidential.

Data from the mobile device (Fitbit™) will be automatically transferred to the Fitbit™ smartphone app. The data are then automatically transferred to the Fitbit™ company servers. These data are not identifiable since we are providing participants with a Fitbit™ login ID that is created by the study team. Data will be maintained on the Fitbit™ servers indefinitely. Data from the Fitbit™ servers will be automatically transmitted to [name] team's mobile health platform (Prompt) at Duke University. The platform compiles and analyzes biological, environmental and behavioral data from mobile devices and sensors. Using these data, algorithms are developed to perform analytics and, in a feedback loop, intervene with patients or their social network, or transmit their data to providers. This software is currently used in NIH-funded trials, including another with Drs. [name]' and [name], and approved by the Duke IRB and security office for clinical trial use.

In this study, participants will sign a consent and HIPAA Authorization (or oral consent will be obtained if the screening/enrollment visit is done remotely) to allow data from the mobile devices to be transmitted to the platform, where it will be aggregated. Interventionists will have access to a dashboard in the software system, where they can view physical activity data from study participants. This will allow the interventionists to provide tailored feedback. All data from the platform will be transferred (with identifiers: phone number and study ID) using IRB-approved methods to the University of Wisconsin-Madison during the data analysis phase of the grant. The data can be used for ancillary analyses to examine patterns of self-monitoring and engagement with the intervention.

In order to prevent the exposure of personal identifying information or PHI, we will use the following procedures:

Page 36 of 52

1. During the screening process, each potential patient and partner will be assigned a study participant number for tracking purposes.
2. Participant identifying information that is recorded on paper will be kept in a locked file cabinet in the research offices at UW-Madison of the PI or WREN.
3. Potential participants who decline participation or are ruled ineligible during the screening process will have all their identifying information destroyed.
4. Case report forms will be identified by study participant number only.
5. No results will be reported in a personally identifiable manner.
6. The recruitment tracking system will be firewalled behind the SMPH firewall, only accessible from SMPH workstations, not the internet in general. SSL (secure socket layer) encryption will be employed to access the site, guaranteeing end to end security. The server physically resides on Surgery's Virtual Infrastructure located in the data center in MFCB behind a locked, keycarded, and PIN required door. The same security measures will be in place for the online screening website except that the website will be accessible from the general internet.
7. All tracking system data will be password-protected with several levels of protection.
  - a. The first password will allow access to the operating system of the computer.
  - b. The second password will allow access to the basic menus of the integrated system. Administrative functions are restricted to only certain ID's. Our prior research employing similar precautions has demonstrated that these techniques are very successful in assuring the protection of participants.
8. Data from the mobile device (Fitbit™) will be aggregated using a software engine designed by Duke software engineers, called Prompt. Prompt is used in many NIH-funded studies at Duke University and has received approval to be used by the Duke IRB. Prompt uses Twilio and Amazon S3. Prompt will receive physical activity data from Fitbit™. We will not collect names in this database, only phone number and study ID of each participant, as well as data from Fitbit™ (physical activity). Study staff will login to a password-protected database to view study ID and see if participants are using the devices. We will use Amazon S3 to store data; data will be encrypted when it is stored. These are companies outside of Duke that will have access to participants' personal information (phone number and data from the devices). If these data are further disclosed by them or their business partners, it may no longer be covered under the privacy protections. [name], UW-Madison HIPAA Security Officer, has vetted and approved these Duke platforms.
  - a. The mobile health platform, Prompt, is password-protected and only the necessary investigators (with Duke IRB approval) will have access to the software and participant data. All data that are exported from the platform will be coded with only the participant study ID linked (not their phone number).
  - b. Data exported from the mobile health platform will sit on a firewall-protected Duke School of Nursing Server in a secure electronic folder (S:\SED\Partner2Lose). Only necessary investigators will have access to this folder.
  - c. This data will be transferred approximately every 6 months to the University of Wisconsin-Madison via a Duke managed Box folder. Once the data are uploaded, the UW will download and store the data to the Department of Surgery (DOS) Instance of REDCap. DOS REDCap will only accessible by members of the UW research team. Each user in DOS REDCap has their own ID and can only see their projects or projects that have been shared with them. The UW Department of Surgery and School of Medicine and Public Health scan for vulnerabilities on a regular basis.
9. We will register all participants with the mobile devices using their coded study ID and a coded e-mail address. For example, for participant 'P1234' we will create a Gmail account [contact]'. This coded e-mail address will be used as the registration for the Fitbit™ and will only be linked to the participant using the secured study key. The participant 'name' in the Fitbit App and at Duke will be the Study ID.
10. We will ensure that all sharing options with third party services such as online social networks or other fitness apps are disabled. Participants will be encouraged not to share information with third party services such as online social networks or other fitness apps. However, some participants may opt to do this. Thus, all participants will be encouraged to read the privacy statement for the mobile devices and to decide for themselves what information they would like to share.
11. The group sessions and maintenance telephone calls will be audio recorded. The recordings will be stored and shared with [name] via a secure Duke box folder. Only members of the research team will have access to these recordings. The audio recordings will not contain identifiers and the study team will discourage the use of identifiers at the beginning of each group session (e.g. ask the participants not to use full names). The recordings will be stored for up to 7 years after the study is completed.
12. DOS REDCap, an approved electronic database that is only accessible by members of the research team, will be used for randomization, enrollment, and questionnaire/survey completion. Each user in DOS REDCap has

their own ID and can only see their projects or projects that have been shared with them. The Department of Surgery and School of Medicine and Public Health scan for vulnerabilities on a regular basis. Participants will be assigned a unique identifier number in this database once they are scheduled for their in-person screening visit. At that time, some of their identifiable information will be entered and stored in DOS REDCap. This unique identifier will be linked to a separately maintained master list that contains participant identifiers, which will be located in the tracking system. This linkage will allow research staff to track the enrollment process. Any additional identifiable information will be coded prior to entry into the final dataset. Consequently, the final dataset that will be retained will not include any participant identifiers.

13. We will use Duke's instance of REDCap to send text messages to participants to encourage them to self-monitor and use the devices. This software interfaces with Twilio to send text messages. We will store participant phone numbers and study IDs in Duke's REDCap, no other information is needed.

- a. Text messaging does not provide a completely secure and confidential means of communication. No PHI will be sent via text message. All of this information is included in the consent form.
- b. Duke's REDCap, is password-protected and only the necessary investigators will have access to the software and participant data. All data in Duke's REDCap will be coded with only the participant ID.
- c. Duke's REDCap will only store phone numbers and study ID codes while the UW-Madison DOS REDCap will store all other study data.

14. For data analysis and safety monitoring, the data will be downloaded from DOS REDCap to the UW secure Biostatistic servers. Data analysis will occur on the secure Biostatistic servers.

15. Access to study data will be removed for all study personnel when they are no longer part of the research team.

16. If it's necessary to have the group classes via a Webex video call, participants will be provided a link to join the call via their desktop or cell phone. Webex is approved for use by UW HIPAA.

17. The OnceHub online scheduling program is a secure and HIPAA compliant website. Participants will only use their name and email to schedule their 6, 12, 18 and 24 month in-person measurements. Only members of the study team will be able to view participant information. Participants cannot see any other participants' information.

### **11.1.1 Confidentiality of Participant Records**

By signing the protocol, the Investigator agrees that the NIH or IRB representative may consult and/or copy study documents in order to verify CRF data. By signing the consent form (or providing oral consent if the screening/enrollment visit is done remotely), the participant agrees to this process. If study documents will be photocopied during the process of verifying CRF information, the participant will be identified by unique code only and full names and similar identifying information (such as medical record number) will be masked.

The Clinical Site Investigators will ensure that the identity of participants will be protected. All study records will be maintained in a secure fashion with access limited to essential study personnel only. All study documents submitted to the Coordinating Center will have identifiers removed other than dates of birth and service and participants will be identified with a site-specific identification number only. The Clinical Site Investigators will maintain, in a secure location, an enrollment log that includes participant identifying information and links participants to their study-specific identification number.

## **11.2 Data Capture**

### **11.2.1 Source Documents**

All source data will be kept and merged and/or entered into the electronic clinical trial software (DOS REDCap). Source data is all information, original records of clinical findings, observations, or other activities in a clinical trial necessary for the reconstruction and evaluation of the trial. Source data are contained in source documents. Examples of these original documents and data records include: surveys recorded on hard copy or in DOS REDCap; ASA24 data; participant files.

Data will be collected during the screening visit, Month 0 (first group session: weight only), Month 6 visit, Month 12 visit, Month 18 visit, Month 24 visit. Data will also be collected during the in-person group visits and telephone calls for the intervention portion of the study.

Data will also be pulled from the mobile device Fitbit™ using our mobile health platform, known as Prompt. The data will be used for research purposes only.

## 11.2.2 Case Report Forms

The study case report form (CRF) is a data-reporting instrument for the study. All data requested on the CRF must be recorded. All missing data must be explained.

- All entries should be printed legibly in black ink.
- If any entry error has been made, to correct such an error, draw a single straight line through the incorrect entry and enter the correct data above it.
- All such changes must be initialed and dated.

NOTE:

- If a space on the CRF is left blank because the procedure was not done or the question was not asked, write "N/D".
- If the item is not applicable to the individual case, write "N/A".
- DO NOT ERASE OR WHITE OUT ERRORS.
- For clarification of illegible or uncertain entries, print the clarification above the item, then initial and date it.

### 11.2.2.1 Missing Data

Our plans for preventing and dealing with missing data follow the guidelines set forth by the National Research Council's Panel on Handling Missing Data in Clinical Trials. First, we will employ numerous strategies to achieve < 20% patient attrition. Second, as recommended by the panel, we will conduct two general types of sensitivity analyses for our primary analysis. Because we are using full likelihood methods, the primary analysis model above (as well as the exploratory aim analysis model discussed below) is valid under the MAR (missing at random) framework, where missing values may depend on treatment arm, any observed weight measurement, patient sex, and patient and partner *month0* weight. If missing values are related to other measured factors, such as physical activity measurements, then multiple imputation provides a framework for incorporating information from these auxiliary variables while still preserving a parsimonious main treatment effect model.(86) As a first sensitivity analysis, a general, multivariate imputation model will be constructed using all observed weights, treatment arm, and any covariates predictive of missingness. The primary model, specified above, will then be fit to the multiply imputed data, and the estimates and standard errors will be combined using appropriate combining rules. We acknowledge the possibility that data may be MNAR and propose as a second sensitivity analysis to explore MNAR methods, including pattern-mixture models and the toolkit of methods presented in O'Kelly & Ratitch.(87)

## 11.2.3 Data Collection Tools

This study will use the Department of Surgery instance of REDCap, which provides data management functionality by allowing the development of eCRFs and surveys to support data capture. DOS REDCap is a secure, web-based, flexible system with an intuitive interface to enter data and has real time validation rules with automated data type and range checks at the time of data entry.

## 11.3 Data Management

UW-Madison will serve as the data coordinating center, overseeing timely and accurate data collection. The data coordinating center agrees to be responsible for implementing and maintaining quality control and quality assurance systems with written standard operation procedures (SOPs) to ensure that trial is conducted and data are generated, documented, and reported in compliance with the protocol, accepted standards of Good Clinical Practice (International Conference on Harmonization E6), and all applicable federal, state, provincial, and local laws, rules, and regulations relating to the conduct of the clinical trial in an ongoing and auditable manner. The DOS instance of REDCap, a web application for managing surveys will be used for data collection of survey instruments and to randomize participants.

## **11.4 Data Monitoring**

DOS REDCap reports will be used to provide up-to-the-minute access to all entered data. This will allow verification of completeness, timeliness, reliability, and accuracy of collection and coding of data. Consistency checks and range checks have been built into the DOS REDCap System.

In preparation for and during ICTR DMC reviews, the DMC staff will notify the study team if any questions regarding data arise. This may include, but is not limited to, missing data elements, outliers, and/or conflicting data points.

## **11.5 Records Retention**

For this non-FDA regulated study, all study data will be retained for at least 5 years after the last manuscript published under this clinical trials protocol number. If the analysis data will be retained beyond this window (example: for another study), a separate protocol and IRB approval will be obtained.

# **12. Assessment of Safety**

This is a minimal risk study. The PI will be notified of any AEs/SAEs and ensure that all notifications (IRB, DSMB, etc.) occur according to protocol.

## **12.1 Specifications of Safety Parameters**

### **12.1.1 Definition of Adverse Events (AE)**

Adverse event means any untoward medical occurrence associated with the use of an intervention in humans, whether or not considered intervention-related (21 CFR 312.32 (a)).

### **12.1.2 Definition of Serious Adverse Events (SAE)**

An AE or suspected adverse reaction is considered "serious" if, in the view of either the investigator or sponsor, it results in any of the following outcomes: death, a life-threatening adverse event, inpatient hospitalization or prolongation of existing hospitalization, a persistent or significant incapacity or substantial disruption of the ability to conduct normal life functions, or a congenital anomaly/birth defect. Important medical events that may not result in death, be life-threatening, or require hospitalization may be considered serious when, based upon appropriate medical judgment, they may jeopardize the patient or participant and may require medical or surgical intervention to prevent one of the outcomes listed in this definition.

### **12.1.3 Definition of Unanticipated Problems (UP)**

OHRP considers unanticipated problems involving risks to participants or others to include, in general, any incident, experience, or outcome that meets all of the following criteria:

- Unexpected in terms of nature, severity, or frequency given (a) the research procedures that are described in the protocol-related documents, such as the IRB-approved research protocol and informed consent document; and (b) the characteristics of the participant population being studied;
- Related or possibly related to participation in the research ("possibly related" means there is a reasonable possibility that the incident, experience, or outcome may have been caused by the procedures involved in the research); and
- Suggests that the research places participants or others at a greater risk of harm (including physical, psychological, economic, or social harm) than was previously known or recognized.

This study will use the OHRP definition of UP.

Corrective actions or changes that will be considered in response to an UP will include:

- Modification of inclusion or exclusion criteria to mitigate the newly identified risks
- Implementation of additional safety monitoring procedures
- Suspension of enrollment of new participants or halting of study procedures for enrolled participants
- Modification of informed consent documents to include a description of newly recognized risks
- Provision of additional information about newly recognized risks to previously enrolled participants.

## 12.2 Classification of an Adverse Event

### 12.2.1 Severity of Event

The following guideline will be used to describe severity:

**Mild** – Events require minimal or no treatment and do not interfere with the participant's daily activities.

**Moderate** – Events result in a low level of inconvenience or concern with the therapeutic measures. Moderate events may cause some interference with functioning.

**Severe** – Events interrupt a participant's usual daily activity and may require systemic drug therapy or other treatment. Severe events are usually potentially life-threatening or incapacitating.

### 12.2.2 Relationship to Study Intervention

For all collected AEs, the clinician who examines and evaluates the participant will determine the AE's causality based on temporal relationship and his/her clinical judgment. The degree of certainty about causality will be graded using the categories below.

**Definitely Related** – There is clear evidence to suggest a causal relationship, and other possible contributing factors can be ruled out. The clinical event occurs in a plausible time relationship to intervention and cannot be explained by other factors.

**Probably Related** – There is evidence to suggest a causal relationship, and the influence of other factors is unlikely. The clinical event occurs within a reasonable time after administration of the intervention and is unlikely to be attributed to other factors.

**Possibly Related** – There is some evidence to suggest a causal relationship (e.g., the event occurred within a reasonable time after administration of the intervention). However, other factors may have contributed to the event (e.g., the participant's clinical condition, other concomitant events). Although an AE may rate only as "possibly related" soon after discovery, it can be flagged as requiring more information and later be upgraded to "probably related" or "definitely related," as appropriate.

**Unlikely to be related** – A clinical event whose temporal relationship to drug administration makes a causal relationship improbable (e.g., the event did not occur within a reasonable time after administration of the trial medication) and in which other behaviors or underlying disease provides plausible explanations (e.g., the participant's clinical condition, other concomitant treatments).

**Not Related** – The AE is completely independent of intervention and/or evidence exists that the event is definitely related to another etiology. There must be an alternative, definitive etiology documented by the clinician.

### 12.2.3 Expectedness

The study clinician will be responsible for determining whether an AE is expected or unexpected. An AE will be considered unexpected if the nature, severity, or frequency of the event is not consistent with the risk information previously described for the intervention.

## 12.3 Time period and frequency for event assessment and follow-up

The occurrence of an AE or SAE may come to the attention of study personnel during study visits and interviews of a study participant presenting for medical care. All AEs, including local and systemic reactions not meeting the criteria for SAEs, will be captured on the appropriate CRF. Information to be collected includes event description, time of onset, clinician's assessment of severity, relationship to study intervention, and time of

resolution/stabilization of the event. All AEs occurring while on study must be documented appropriately regardless of relationship. All AEs will be followed to adequate resolution.

Any medical condition that is present at the time that the participant is screened will be considered as baseline and not reported as an AE. However, if the study participant's condition deteriorates at any time during the study, it will be recorded as an AE. UPs will be recorded in the data collection system throughout the study.

Changes in the severity of an AE will be documented to allow an assessment of the duration of the event at each level of severity to be performed. AEs characterized as intermittent require documentation of onset and duration of each episode.

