#### Partner

- underweight BMI (i.e., BMI < 18.5 kg/ m^2)
- residing in a nursing home or receiving home health care
- impaired hearing
- any severe health issue that would impair the partner's ability to provide support, including
  - significant dementia, drug or alcohol abuse, or unstable psychiatric illness (e.g., schizophrenia or psychosis)
  - current treatment for cancer or being treated for cancer (beside skin cancer) in the last 6 months
  - In the last 6 months prior to screening:
    - acute coronary syndrome (ACS) including STEMI (ST-elevation myocardial infarction), NSTEMI (non-ST elevation myocardial infarction) and unstable angina (UA)
    - recent or impending coronary revascularization [recent coronary bypass grafting (CABG) or percutaneous coronary intervention (PCI)]

- unstable arrhythmia (e.g., hospitalized for unstable atrial fibrillation, supraventricular tachycardia, ventricular tachycardia, ventricular fibrillation and/or firing of implantable cardiac defibrillator [ICD])
- recent acute congestive heart failure exacerbation [requiring increased doses of oral or intravenous (IV) diuretics or hospitalization]

Given population rates of overweight/obesity and the fact that weight and health behaviors are highly correlated within couples, it is possible that both members of a couple will be eligible to be index patients. If both partners in a household desire and are eligible for the patient intervention, then we will ask them to decide which one will be the index patient. Partners may choose to make similar behavior changes as patients; however, partner behavior change is not the focus, and partners in the patient-only arm will receive no intervention. Because partner outcomes are of potential interest to society and to payers, and because previous studies targeting patients have observed “ripple” effects,(36) we will analyze partner outcomes.

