### **Partner involvement in weight loss initiation intervention (months 1-6)**

The partner intervention will be delivered by the interventionist and, as explained in C.9, will be supplemented with text messages to reinforce support principles and support commitment. There is no literature to suggest the optimal dose of a partner intervention. We are using our experience in dyadic interventions to strike the balance between efficacy and burden, which will be achieved by a combination of partners participating in a subset of group and telephone patient intervention contacts and receiving supplemental text messages. Partners are not requested to attend all 12 biweekly patient sessions, as burden may lead to attrition. Instead, they will attend 6 monthly meetings. Monthly contacts led to meaningful patient behavior change in our previous trials. The month 1 partner meeting will be conducted at the same time as the patient meeting with the goals of orienting partners to the intervention, introducing social support principles, and providing example behaviors that are likely to be perceived as bilateral and supportive versus unilateral and unsupportive. For example, partners will be taught to provide empathy and avoid making comments that can be perceived as critical; comment on positive rather than negative patient behaviors; make the same lifestyle changes when possible; offer praise; and help patients reward themselves for goal achievement.

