#### **Partner involvement in weight loss maintenance intervention (months 7-18)**

Month 7 will involve partner attendance at the three patient group sessions led by the interventionist, which includes an overview of the patient maintenance program and a discussion of the partner's role in weight maintenance. Partners will co-participate in the three monthly calls in months 7-9 because it is important for partners to learn to work together effectively to promote patient behaviors that maintain weight loss and to receive coaching from the interventionist if challenges are encountered. Partners will also participate in calls in months 12 and 18. During all joint telephone calls, partners and patients will co-develop patient relapse plans and partner support plans. They will be encouraged to communicate regularly about the identified plans, assess progress, and work together to overcome barriers. Calls to couples will be ~10 minutes longer than patient-only calls. In the CouPLES trial, patients and spouses participated on >75% of calls together even though the protocol did not require it; thus, we expect high compliance in this study.

The content from the group sessions and maintenance telephone calls will be revised iteratively until the team feels that patients understand and can engage with the content. Changes may be made to enhance comprehension of intervention material or the ability to engage in the recommended behavioral skills.

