### **12.4.1 Adverse Event Reporting**

Adverse events must be reported once the participant undergoes any study procedures and adverse events must be reported during the entire active study period. The IRB, DMC, and NIH will receive notifications about AEs.

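### With no scheduled adverse event question and 18 versus 4 live partner contacts by arm, partner events are liable to be over-ascertained in the partner-assisted arm, and the by-arm rates do not separate partners from patients

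*Combined protocol and SAP*

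**What the plan says.** **Capture.** Section 12.3 says: "The occurrence of an AE or SAE may come to the attention of study personnel during study visits and interviews of a study participant", the sentence ending with a reference to presenting for medical care. The duty to record is broad. Section 12.3 adds that "All AEs occurring while on study must be documented appropriately regardless of relationship", and section 12.4.1 that "adverse events must be reported during the entire active study period". Table 2 (section 9.2), the outcome-visit text (section 9.2.1) and Table 7 (section 9.2.3) list what is collected at each time point; none lists an AE question.

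**Partner contact.** For months 1-6 in the partner-assisted arm, section 9.2.2 says of partners: "Instead, they will attend 6 monthly meetings". For maintenance: "Month 7 will involve partner attendance at the three patient group sessions led by the interventionist". Partners also join the three calls in months 7-9, and "Partners will also participate in calls in months 12 and 18". By contrast, the end of section 8.3 states that "partners in the patient-only arm will receive no intervention". Both members of every couple are due at outcome visits at months 6, 12, 18 and 24.

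**Use of the data.** Section 10.4: "Safety reports will tally adverse events by intervention assignment and postulated relationship to the trial interventions; event rates will be reported per person year". The same paragraph provides for stopping the study if the Data Monitoring Committee (DMC) review finds excessive risk. It does not say whether partner events are counted, or whether patients and partners are tabulated separately.

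**The concern.** When events are found passively, the number found depends partly on how often staff and participants meet. Here that opportunity differs by arm for one class of participant. Interventionists, who make the extra partner contacts, are also unblinded: section 12.7 blinds only the outcome assessors.

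If partner events enter the by-arm rates, equal true risk could show as a higher rate in the partner-assisted arm. A pooled table would give the DMC no direct way to see whether an excess came from patients, whose contacts are equal in number, or from partners, whose contacts are not. Events among patient-only partners could be under-recorded without anyone noticing. The primary outcome is not affected.

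**Working it through.** The plan gives no figure for AE ascertainment, so there is none to reproduce. The check is a count of contacts, then an illustration of size.

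**1. Live partner contacts after the disclosure session** (section 9.2.2 text, checked against Table 3)

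| Contact | Partner-assisted | Patient-only |
|---|---|---|
| Monthly group meetings, months 1-6 | 6 | 0 |
| Maintenance group sessions | 3 | 0 |
| Joint calls, months 7, 8, 9 | 3 | 0 |
| Joint calls, months 12, 18 | 2 | 0 |
| Intervention subtotal | 14 | 0 |
| Outcome visits, months 6, 12, 18, 24 | 4 | 4 |
| Total | 18 | 4 |

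The text places the three maintenance sessions in month 7 and Table 3 places them in months 7, 8 and 9; the count is the same.

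**2. Patient contacts.** Table 3 lists 13 initiation sessions, 3 maintenance sessions and 9 calls: 13 + 3 + 9 = 25 in each arm. Leaving out the disclosure session gives 24. (The partner text in section 9.2.2 speaks of 12 initiation sessions, which also gives 24 with the disclosure session counted.) Adding four outcome visits gives 28-29 in both arms. Joint calls are about 10 minutes longer, but not more numerous.

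**3. Couple totals.** With 28 patient contacts: 28 + 18 = 46 versus 28 + 4 = 32, ratio 46/32 = 1.44. With 29: 47 versus 33, ratio 1.42. These ratios would apply to pooled rates only if detection were proportional to contacts.

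**4. Illustration of size.** Assume the same true AE rate in both arms and in both roles, and events spread evenly over 24 months. Let each contact falling within w months after an event capture it with probability q. For an event at time t, let k(t) be the number of contacts from t to t + w. Then

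capture = average over t of [1 − (1 − q)^k(t)].

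Contacts were placed at approximate scheduled times, using 28 per patient. The documents give neither q nor w; q was varied from 0.3 to 1.

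| Look-back w | Ratio, partners only | Ratio, patients and partners pooled |
|---|---|---|
| 1 month | 3.0 to 4.0 | 1.41 to 1.43 |
| 3 months | 1.5 to 2.9 | 1.18 to 1.40 |
| 6 months | 1.0 to 2.0 | 1.00 to 1.31 |
| 24 months | 1.0 to 1.3 | 1.00 to 1.12 |

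The low end of each range is q = 1 and the high end is q = 0.3.

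Two cells can be checked by hand. For w = 6 and q = 0.3, each event in a patient-only partner has one visit within reach, so capture is 0.30. Capture is 0.61 for partner-assisted partners and 0.69 for patients, so the pooled ratio is (0.61 + 0.69)/(0.30 + 0.69) = 1.31. For w = 6 and q = 1, every event meets a visit in both arms, capture is 100% and the ratio is 1.00.

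No combination gave a ratio below 1.

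**The case against.** **Passive wording is not exclusive wording.** Section 12.3 says how events may surface, not that this is the only route, and it requires all AEs to be entered on a case report form. Section 9.2.5 ends AE follow-up at the final outcome visit, which suggests that it runs through that visit in both arms. The case report forms, the manual of procedures and the attached surveys are not reproduced in the text reviewed and may contain a prompt. This stands: absence from two tables and the visit text does not prove that nothing is asked. If a prompt exists, section 12.3 should say so.

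**Some contact is common to both arms.** Both members of every couple receive surveys at months 3, 9, 15 and 21. Counting these gives partners 18 + 4 = 22 versus 4 + 4 = 8, and couples, on the 47 versus 33 count, 55 versus 41, a ratio of 1.34. The contrast shrinks but remains, and no AE item is listed for those surveys either.

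**The contact ratio is not an estimate.** A joint session counts once for each spouse, although the occasions on which staff meet at least one member of a couple are equally many in both arms. Nine of the 14 extra contacts are group sessions, where section 5.4.3 advises people to share only what they are comfortable saying in public. A reader might infer that the partner-assisted rate will look about 42% too high. The documents do not support that: the figure needs detection proportional to contacts, which nothing in them establishes.

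**Only partner events are affected, and they may not be counted.** Sections 2 and 7.1 count 460 people, which includes partners; section 15.3 names partners separately from participants. If partner events are left out of the rates, the imbalance largely disappears. This stands, and is a reason to state the rule.

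**The DMC has other information.** Section 10.4 also tallies events by postulated relationship and sets no by-arm threshold or test. The DMC reviews all serious events and may examine source documents. A reader might infer that it could not tell harm from surveillance, or would be led to stop the trial wrongly; the documents do not support either. They show only that the planned rates lack the split that would make the question easy to answer.

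**Conclusion.** The concern holds as a risk of differential ascertainment, not as a demonstrated bias. What is documented is passive wording, no scheduled AE question in the tables or visit text, 18 versus 4 live partner contacts, and by-arm rates with no split by role. The direction follows from the counts: any distortion from this source would raise the partner-assisted rate.

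The size is unknown. The pooled ratio of 1.00 to about 1.4, and the partners-only ratio of 1.0 to about 4.0, rest on assumed capture probabilities and look-back periods, on equal true rates in both arms and roles, and on partner events being included. The ratio is 1.00 if events are fully elicited at the common visits. In a trial that the protocol classes as minimal risk, this is a worthwhile, inexpensive improvement to safety reporting and does not bear on the efficacy analysis.

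**What to change.** 1. In section 12.3, Table 2 and Table 7, add the same AE question for patients and partners in both arms at months 6, 12, 18 and 24, covering the time since the previous assessment. Put it on the existing REDCap survey link, so that blinded outcome assessors are not exposed to answers that reveal the arm. Where surveys are completed at the visit instead, keep this item self-completed and have other staff read the replies.
2. In section 10.4, state that partner events are included. Tabulate by-arm rates separately for patients and partners, and by source: solicited at the common assessments, or reported at intervention contacts.
3. Use the solicited rates for the like-for-like arm comparison. Show the all-source rates and all serious events alongside; solicited rates alone could hide real harms first reported at a session or call.

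The cost is one question on assessments that already take place, somewhat more minor AEs to record and review, and a few more table rows. Intervention content, visit numbers and the efficacy analysis are unchanged.
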